Appendix 8: Compensation Form

Page 1

Baseline Compensation

Record ID _____

Compensation Date _____

Compensation Amount _____

Voucher Number _____

Compensation Intern [name]
 [name]
 [name]

Notes _____

Appendix 9: Group Assignment REDCap Form

Page 1

Group Assignment

Record ID

Participant was assigned to

- Intervention group
- Control group

Appendix 10: Pharmacist REDCap Forms

Scheduling Call

Record ID

Date of Scheduling Call

Time of Scheduling Call

Encounter Outcome

- Complete - spoke with patient
- Complete - spoke with proxy
- Complete - revised appointment date/time
- Incomplete - no answer, left message
- Incomplete - busy signal/no voicemail
- Incomplete - wrong number

Note

Follow Up

Date

Time

Form Author

Patient Follow Up

Record ID

Encounter Date

Contact Type

Patient Other (explain in comments below)

Contact Type Comments:

Encounter Length

(minutes)

Encounter Notes

Barriers/Side Effects

Barriers to Regimen/Side Effects

Adherence

of missed doses in the past week

Use of adherence tools

Medication cost concerns

Assessment/Plan

BP Goal

Patient is/is not at goal.

is
 is not

Lifestyle Changes Recommended to Patient

Lifestyle changes recommended to patient: (check all that apply)

- decrease weight
- DASH plan
- Other diet recommended
- reduce sodium
- increase activity
- decrease smoking
- increase med compliance
- other
- no lifestyle changes recommended

If other, specify here: _____

New Plan/Recommendations

New plan/recommendations

Continue current regimen
 Recommend change to plan

If recommending change to plan, list complete plan here: _____

Include:

- 1) Prescribed medication
- 2) Medication code
- 3) Change Type (a = drug started, b = dose increased, c = dose decreased, d = drug discontinued)
- 4) Dose 1
- 5) Dose 2
- 6) Unit
- 7) Frequency
- 8) Comments

Follow Up Information (if applicable)

Date

Follow Up Time_____
Follow up purpose:

Form Author

Physician Communication

Record ID

Encounter Date

Encounter Mode

EMR Email Fax Other (explain in comments below)

Encounter Comments

Provider Name

Physician Acceptance

Recommended plan accepted Recommended plan modified (list complete final plan below)
 Plan not accepted, continue previous plan

Final Plan (complete only if changed from pharmacist recommended plan)

Include:

- 1) Prescribed medication
- 2) Medication code
- 3) Change Type (a = drug started, b = dose increased, c = dose decreased, d = drug discontinued)
- 4) Dose 1
- 5) Dose 2
- 6) Unit
- 7) Frequency
- 8) Comments

Recommendation Outcome Date

Follow Up Information (if applicable)

Date

Time

Form Author

Appendix 11: 12 Month Exit Survey

Page 1

12 Month Exit Survey

Record ID _____

Blood Pressure Measurement

How difficult was it for you to measure your blood pressure?	 Extremely difficult  Difficult  Neutral  Easy  Extremely easy  I prefer to not answer
How difficult was it for you to text us your blood pressure values?	 Extremely difficult  Difficult  Neutral  Easy  Extremely easy  I prefer to not answer
How often would you be willing to continue text your blood pressure values to your health care provider?	 Once per day  Once per week  Once per month  Once every 3 months  Once every year  I prefer to not answer

Pharmacist Questions

My contact(s) with the research pharmacist were	 Extremely unhelpful  Unhelpful  Neutral  Helpful  Extremely helpful  I prefer to not answer
I would find it helpful to continue having contact with the research pharmacist after the study is over.	 Yes  No  Unsure  I prefer to not answer

Feedback Responses

What suggestions do you have about the process of measuring your blood pressure and texting it to us?

What problems, if any, did you have measuring and texting your blood pressure values?

What feedback do you have about the research pharmacist?

Appendix 12: Patient-Reported ER Visits or Hospitalizations

Page 1

Patient-Reported ER Visits or Hospitalizations

Record ID

Has the patient had any emergency room visits or been hospitalized during the 12 months of study follow up outside of the University of Iowa system?

Diagnosis/Reason

(Record N/A if patient did not have any visits during this time.)

Date

Research intern who collected outside visits/hospitalizations.

- [name]
- [name]
- [name]
- [name]
- [name]
- [name]

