Study Title: A Pharmacist Intervention for Monitoring and Treating Hypertension Using Bidirectional Texting

Version Number/Amendment	Approval Date
Original Protocol, Version 1.0	8/3/2019
Revised Protocol, Version 2.0	11/27/2019
Revised Protocol, Version 3.0	12/30/2019
Revised Protocol, Version 4.0	7/17/2020
Revised Protocol, Version 5.0	9/21/2020

Protocol Synopsis

Protocol Title	A Pharmacist Intervention for Monitoring and Treating Hypertension Using Bidirectional Texting
Main Criteria for Inclusion	Clinic measured blood pressure of ≥ 145 mmHg or ≥ 95 mmHg at two previous clinic visits or one previous clinic visit and on the day of enrollment. Previous clinic visit BPs must be within the past 18 months and measured at least 2 weeks apart from each other.
Study Objective	To evaluate whether our scalable SMS approach combined with a pharmacist-based intervention improves BP management and that is cost effective.
Study Design	A single-site, two-arm, single-blind randomized trial
Number of Sites	1 site, 3-4 clinic locations
Study Arms	2 Study Arms a) Intervention Group- Text 7 morning and 7 evening BP values at baseline. Monitored by a study pharmacist for 12 months. Research visits at 6 and 12 months b) Control Group- Text 7 morning and 7 evening BP values at baseline. Research visits at 6 and 12 months
Total Number of Subjects	420
Duration of Study Participation	12 months
Primary Outcomes	Mean difference in systolic blood pressure between the control and intervention groups at 12 months.
Secondary Outcomes	Mean difference in diastolic blood pressure between the control and intervention groups at 12 months. Total number of medication changes (i.e., dose, discontinuation, initiation, etc.) from baseline to 12 months.

	Total cost of medications, time spent by research staff, and clinic visits per patient from baseline to 12 months.

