All participants will be asked to return to the clinic where they enrolled at for a 6-Month appointment with a research intern. To allow for flexibility with scheduling, 6-Month appointments will be allowed to occur anytime between 5 Months and 7 Months after the enrollment date. This BP value will be the outcome BP value. If a participant is not able to make it to the clinic during this window, but does want to come in after the 7 Month date, this will be allowed and all data will be collected, however, it will not be counted in the 6-month outcome and the 6-month outcome will be considered missing. In this case, a note will be placed in the participant's record and these data may not be used in analyses.

At the 6-Month appointment, the research intern will collect the research BP values, any BP medications that the participants are currently taking, the last 3 BP values that were

recorded by the participant's home BP cuff, and test the home BP cuff for accuracy. If the home BP cuff appears to be measuring inaccurately, it will be replaced. The participant will be sent another \$50 compensation check. All of the procedures outlined at baseline will be followed again, but the data will be collected on separate 6 Month REDCap forms (not shown).

4.6 12-Month Visit Procedures

All participants will be asked to return to the clinic for a 12-Month appointment with a research intern. To allow for flexibility with scheduling, 12 Month appointments will be allowed to occur anytime between 11 Months and 13 Months after the enrollment date. If a participant is not able to make it to the clinic during this window, these data will be missing.

At the 12-Month appointment, the research intern will collect the research BP values, any BP medications that the participants are currently taking, a 12-Month Exit Survey (Appendix 11) asking for the participant's feedback about the study, and send another \$50 compensation check. All of the procedures outlined at baseline will be followed again, but the data will be collected on separate 12-Month REDCap forms (not shown). Participants will also be asked about any hospitalizations or emergency room visits that occurred over the 12-month follow up period, especially those that occurred outside of the University of Iowa system (Appendix 12).

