Our working hypothesis is that there will be a greater number of medication changes in the intervention group compared to the control group. We will count the number of medication changes (dose increased, dose decreased, drug stopped, drug started) during the 12 months following the start of the intervention. The total number of medication changes will be the primary outcome measure for Aim 2. In addition, we will determine the number of pharmacist recommendations that were accepted by physicians. These are process measures: we found in our previous studies that BP improvement was primarily related to medication changes. We are assuming that changes are a sign of close monitoring. Indeed, we have used this measure previously. However, we realize that not all medication changes are equal, and thus we will record both medication trends and final treatment for each patient.

Aim 3: Determine the cost effectiveness of the intervention.

Our working hypothesis is that our intervention will be cost effective when compared to the control group. In addition, we will compare these results to previous pharmacist interventions. Because much pharmacist time is spent on non-direct patient care activities, we are convinced that our bi-directional texting approach will be both labor and cost saving. We will compute the incremental cost effectiveness ratio (ICER) using the total costs of doctor visits, pharmacist time, medications and medication changes during the 12 months of the trial. The ICER will be the difference between the control and intervention groups in average total cost

divided by the difference in average decrease of SBP and DBP. The ICER will be expressed in the dollars per mmHg reduction in BP and will be the primary outcome in this Aim.

6. Statistical Design and Power

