Aim 3 Analysis: The analysis will be performed on an intent-to-treat basis regardless of the number of reported BP measurements or the number of pharmacist interactions with the subject. The perspective of this cost analysis is society in general. For each patient encounter, pharmacists will record the number of minutes spent in the following activities: medical record review, consultation, patient assessment, ordering medications, medical education, lifestyle education, BP measurement education, making recommendations, and documentation in the medical record. Pharmacist costs will be estimated by multiplying the time spent by their compensation rate. Costs for clinic visits will be obtained from the university. Utilization measures will be converted to costs per subject using the Medicare fee schedule for visits. Pharmacist and physician salaries will be obtained from the Bureau of Labor Statistics. The average wholesale drug cost for prescription medications will be obtained from Lexicomp Online (<https://online.lexi.com>). Generic prices will be used when available. The drug cost per prescription for each subject will be calculated by multiplying the average wholesale price (AWP) by frequency and dose.

We assume that subjects in the intervention and control groups will have similar characteristics. However, if there are significant differences between the subjects in these groups, costs will be predicted using a multivariate generalized linear model with a gamma family and a log link to control for these differences.

We will determine the cost of the intervention by subtracting the average total cost (pharmacist, clinic, and drugs) for the intervention group from the average total costs for the control group. The ICER is calculated as the cost differential from the intervention divided by the outcome differential from the intervention. Our primary outcome will be average decrease in SBP, and the outcome differential will be the average decrease in SBP for the control group minus the average decrease in SBP for the intervention group. The result of this analysis will be an ICER, which gives the additional cost of the intervention per mm Hg of SBP decrease.

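### Clinic visits enter the ICER from a societal perspective, but no procedure or form shown asks about clinic visits outside the university system, and no rule links a logged visit to a fee

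*Combined protocol and SAP*

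**What the plan says.** **Cost definition.** Section 5 (Aim 3) computes the ICER "using the total costs of doctor visits, pharmacist time, medications and medication changes during the 12 months of the trial". Section 6 (Aim 3 Analysis) forms the cost difference from the "average total cost (pharmacist, clinic, and drugs) for the intervention group" and its control counterpart, and states: "The perspective of this cost analysis is society in general". The Synopsis lists as a secondary outcome: "Total cost of medications, time spent by research staff, and clinic visits per patient from baseline to 12 months".

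**Prices.** Section 6 gives two adjacent statements: "Costs for clinic visits will be obtained from the university" and "Utilization measures will be converted to costs per subject using the Medicare fee schedule for visits".

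**Counts.** Under Section 4.6, a chart review done separately from the 12-month visit logs clinic and quick-care visits, ER visits and hospital stays. The Appendix 13 form for clinic and quick-care visits holds Record ID, diagnosis, date and the intern who recorded the visit.

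**Outside care.** Section 4.6 has participants asked at 12 months about "any hospitalizations or emergency room visits that occurred over the 12-month follow up period", with emphasis on events outside the university system. Appendix 12 is the matching form and asks whether "the patient had any emergency room visits or been hospitalized during the 12 months of study follow up outside of the University of Iowa" system.

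**The concern.** The plan recognises that the university's record may not show care received elsewhere, which is why it asks participants directly. The question covers the two kinds of care that the ICER definition does not list and leaves out the one kind that it does. Under a societal perspective a clinic visit counts wherever it takes place.

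Visits could plausibly differ by arm. Section 4.4.1 has pharmacists advise control participants with raised home readings to book an appointment with their physician. In the intervention arm, medication changes go to the physician through the electronic record. If part of that difference falls outside the reviewed record, the incremental cost is off by that part.

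Pricing is a second, smaller gap. Clinic and quick-care visits share one form with no field to tell them apart, and two price sources are named without a rule for applying them. The planned sensitivity analyses in Section 6 vary drug prices and the valuation of pharmacist time. They do not vary visit counts or visit prices, so neither gap would show up there.

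**Working it through.** The documents give no expected visit count, visit price or ICER, so there is no planned figure to reproduce. The check compares what the ICER needs with what is collected.

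| Care | Listed as an ICER cost? | In the reviewed record | Outside the university system |
|---|---|---|---|
| Clinic and quick care | Yes, as doctor visits (Section 5) or clinic (Section 6, Synopsis) | Appendix 13: diagnosis, date | Not asked in any procedure or form shown |
| ER | Not listed | Appendix 13: diagnosis, date | Asked (Section 4.6, Appendix 12) |
| Hospital stay | Not listed | Appendix 13: diagnosis, admission date, days | Asked (Section 4.6, Appendix 12) |

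The outside-care column is filled for the rows the ICER does not list and empty for the row it does.

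**Sensitivity of the ICER to uncounted visits**

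Inputs from Section 6 (Power): expected SBP decreases of 17.3 mmHg (intervention) and 11.6 mmHg (control). The difference is 17.3 − 11.6 = 5.7 mmHg. The rounded 5.65 mmHg that the plan also gives changes little.

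Formula: shift in ICER = (between-arm difference in uncounted visits per participant × cost per visit) / 5.7.

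- Per $1 of between-arm difference: 1 / 5.7 = $0.18 per mmHg.
- Low end (assumed 0.25 visits at $50): 12.5 / 5.7 = $2.19 per mmHg.
- Middle (assumed 1 visit at $100): 100 / 5.7 = $17.54 per mmHg.
- High end (assumed 2 visits at $200): 400 / 5.7 = $70.18 per mmHg.
- Equal uncounted cost in both arms: 0 / 5.7 = $0.

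Visit differences and prices here are assumptions chosen to show scale. The direction is also open. If controls have more uncounted outside visits, the intervention's incremental cost is overstated; if intervention participants have more, it is understated.

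**Link from visit to fee**

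A logged visit carries Record ID and date. The screening form (Appendix 3) holds the medical record number, and the consent discussion in Section 4.2 covers record data to 12 months after enrollment. Linkage of a visit inside the system to university cost data is therefore possible. No section says that it will be done, or which fee-schedule category a visit receives if it is not.

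**The case against.** The strongest reply is that the forms were never meant to carry costs. Section 6 takes clinic costs from the university and names the Medicare fee schedule, so the Appendix 13 form need only supply counts and dates. This stands. A reader might infer that the forms cannot yield visit costs at all, or that every visit must take one price. The documents support neither reading: linkage is open and no flat price is prescribed. What remains is an unstated rule.

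Second, the visits most likely to differ by arm may well be in the reviewed record. Participants are recruited from patients scheduled at participating clinics, and controls are sent to their own physician. Rural residence alone does not show use of other clinics. This weakens the case for a large bias but does not close the gap, because the documents do not say whether the record shows outside visits.

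Third, a reader might say that outside clinic visits are never captured. That goes too far. The separate 6- and 12-month forms are not shown, and the record might display some outside care. The finding covers only the procedures and forms shown.

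Fourth, Appendix 12 has no field for event type or days in hospital, and non-attenders at 12 months give no answer. It is tempting to count these against the ICER. As defined, the ICER lists no ER or hospital cost, and clinic visits in the record are reviewed for each participant without a visit. These points matter only if ER and hospital costs are to enter the ICER.

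**Conclusion.** The mismatch is confirmed. Clinic visits are an ICER cost under a societal perspective, yet the only outside-care questions shown concern ER visits and hospital stays. Outside clinic and quick-care visits are left uncounted unless the reviewed record happens to show them. The rule from a logged visit to a fee is also missing.

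The size is unknown. The $2 to $70 per mmHg range rests wholly on assumed visit differences (0.25 to 2 per participant) and prices ($50 to $200), and the shift is zero if uncounted costs are equal by arm. A reader might conclude that the incremental cost is distorted; the documents show only that it could be. The point touches one component of a secondary outcome and leaves the primary SBP comparison unaffected. It is worth making because the remedy is cheap.

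**What to change.** 1. Add outside clinic and quick-care visits (type and date) to the Appendix 12 question at the 12-month visit, and preferably ask it at the existing 6-month visit too. The plan allows for 14% attrition, about 59 of 420 participants (0.14 × 420 = 58.8). A 6-month question would recover part of the answer for those lost after that visit. Otherwise, restrict the stated perspective to the university health system.
2. Add a visit-type field to the Appendix 13 clinic form, or specify the match to university cost data by Record ID and date. Either way, state when the university cost applies and when the Medicare fee applies.
3. State whether ER and hospital costs enter the ICER. Only if they do, add event type and days in hospital to Appendix 12.

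The cost is a few REDCap fields, about a minute of interview at visits already planned, slightly longer chart abstraction if the visit-type field is chosen, and some recall error in the self-reported visits.

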Additionally, the research team will conduct a 12-Month Medical Record Review for each participant. This chart review will occur separately from the 12-Month visit and will not require any effort on the part of the participant. A member of the research team will screen the participant's medical record for all clinic/quick care visits (documenting reason), any emergency room visits (documenting reason), and any hospitalizations (documenting reason and length of stay). These data will be recorded on the REDCap forms in Appendix 13. Again, multiple entries will be allowed by REDCap.

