4.7 Adverse Event Reporting and Determination

As this is a low-risk study, we do not anticipate many adverse events. However, if any member of the research team becomes aware of a potential adverse event, they will report it to [name] ([contact]). He will review the event and make a ruling as to whether the adverse event is related to the study or not. If he determines that an adverse event has occurred, the DSMB and IRB will be notified as quickly as possible. Until an official ruling has been made by [name], other members of the research team should not be notified, because they are blinded to group assignment.

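### Outside-system ER visits and hospitalizations have one planned inquiry, at the 12-month visit, so capture depends on attending it and earlier detection is likely to differ by arm

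*Combined protocol and SAP*

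**What the plan says.** Section 4.6 schedules the patient-reported question at the 12-month visit: "Participants will also be asked about any hospitalizations or emergency room visits that occurred over the 12-month follow up period", with emphasis on events outside the university system. The form, Appendix 12, is limited to outside events and asks about "any emergency room visits or been hospitalized during the 12 months of study follow up outside of the University of Iowa system". It has one reason field and one date field.

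The 12-month visit may take place "anytime between 11 Months and 13 Months after the enrollment date". Of those who miss it, section 4.6 says: "If a participant is not able to make it to the clinic during this window, these data will be missing". No telephone, mail or exit contact is offered instead.

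The 6-month visit is held in both arms (section 4.5, Appendix 2). Its items begin: "At the 6-Month appointment, the research intern will collect the research BP values, any BP medications that the participants are currently taking". The list goes on to the last three home-cuff readings and a cuff check. The visit otherwise repeats the baseline procedures, and neither section 4.3 nor the baseline form in Appendix 5 asks about ER visits or admissions. Section 4.5 adds that "the data will be collected on separate 6 Month REDCap forms (not shown").

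Events inside the system come from the 12-Month Medical Record Review in section 4.6, done for every participant. It covers clinic visits, ER visits and "any hospitalizations (documenting reason and length of stay"), entered on the separate forms of Appendix 13. Nothing says that it reaches outside records.

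Section 4.7 starts when a team member becomes aware of a possible adverse event. Once an event is determined, "the DSMB and IRB will be notified as quickly as possible".

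**The concern.** The sponsor evidently expects some outside-system events, since Appendix 12 exists only for them. Three weaknesses follow from asking once, at the end.

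- Capture depends on attending the last visit. In-system events are reviewed for everyone, while outside events are known only for those who come at months 11 to 13.
- Before then nobody is scheduled to ask. Section 4.4 gives controls one early pharmacist contact. Intervention participants are typically contacted every 2 weeks while BP is uncontrolled and at least every 2 months afterwards. An outside admission is therefore more likely to come up in conversation in the intervention arm. A safety tally taken before month 12 could differ between arms because of detection alone.
- At the interim review, participants who have not reached month 12 will not have been asked about outside events.

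A smaller point is that Appendix 12 puts ER visits and admissions in one entry without length of stay, while Appendix 13 separates them and records days in hospital.

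**Working it through.** **Inputs.** Sample size 420, built from 180 per arm plus a 14% allowance (Synopsis and section 6). Dropout in the earlier trial: 13.4% in controls and 14.0% in the intervention arm, the latter over 9 months (same places). Visit windows: 5 to 7 and 11 to 13 months (sections 4.5 and 4.6).

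**The plan's own figure.** 180 / (1 − 0.14) = 209.3, rounded up to 210 per arm, or 420 in total. This reproduces. It serves here only as the base for counting people.

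**Participants with no planned source for outside events.**
- Flat 14%: 420 × 0.14 = 58.8, about 59, leaving 361.2 who are asked.
- Arm-specific rates: 210 × 0.134 + 210 × 0.140 = 28.1 + 29.4 = 57.5, about 58.
- If the 9-month rate is carried to 12 months at constant hazard and applied to both arms (an assumption): 1 − 0.86^(12/9) = 0.182, and 420 × 0.182 = 76.5, about 77.

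**Lag from event to first planned inquiry.** Assume events are spread evenly over follow-up and are not mentioned earlier.
- One question at month T: the mean lag is T/2. For T = 11, 12 and 13 this gives 5.5, 6.0 and 6.5 months, and the longest lag is T.
- Questions at months 6 and 12: the mean lag is 6/2 = 3 months and the longest is 6. With the visit windows, the longest gap between questions is 13 − 5 = 8 months.

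**What a 6-month question recovers among leavers.** Assume dropout is even over 12 months and that those who leave after month 6 attend the 6-month visit.
- Leave after month 6: 58.8 / 2 = 29.4 people.
- Person-months recovered: 29.4 × 6 = 176.4.
- Leavers' total over the 12-month period: 58.8 × 12 = 705.6.
- Share recovered: 176.4 / 705.6 = 25%.

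These figures count people and time, not events. The documents give no rate of outside ER visits or admissions, so the number of events missed cannot be estimated.

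**The case against.** The strongest reply is that no planned estimate uses these data. ER visits and admissions are not a primary or secondary outcome. Aim 3 totals pharmacist, clinic and drug costs. No between-arm count, and no pooling of Appendix 12 with Appendix 13, is specified. This stands: the SBP analysis, the sample size, Aim 2 and the ICER as defined are untouched.

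A reader might infer that the plan breaks its own promise of prompt safety reporting. The documents do not support that. Section 4.7 governs notification after an event is known and determined. An event volunteered or noticed earlier still goes through it at once, and nothing makes Appendix 12 the safety-reporting instrument. The lags above apply to planned inquiry only.

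Late ascertainment is also not peculiar to outside events, because the in-system review is itself a single look at 12 months. What is peculiar to outside events is that they have no source at all when the visit is missed.

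It would also be too strong to say that outside and in-system events cannot be combined by type. The reason field may reveal whether an entry was an ER visit or an admission. Length of stay, however, has no field.

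Two further limits stand. The 6-month forms are not reproduced, so the statement that there is one inquiry rests on the described procedures. And clinics lie within 35 miles of the university hospital (section 4.1), so outside use may be modest. Rural residence points the other way, but the documents settle neither.

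Pharmacist contact and record access in the intervention arm are a real alternative route to detection. Because controls lack the same contact, this supports the arm-balance concern rather than answering it.

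**Conclusion.** The point holds as a limitation in the completeness, timeliness and arm balance of safety and utilization data. About 59 of 420 participants would have no planned source for outside-system events at 14% attrition (58 at the arm-specific rates, about 77 under the constant-hazard extension). For those who are asked, the mean lag to the first planned question is about 6 months if events are evenly spread. Detection before then is passive and likely to favor the intervention arm; its size cannot be derived from the documents. The DSMB's view of outside events at the interim review is incomplete for the same reason.

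This does not undermine the primary result. It is an inexpensive improvement worth making, and the case for it is earlier ascertainment that is more even between arms.

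**What to change.** - Section 4.5: add the Appendix 12 question to the 6-month visit in both arms, covering events since baseline. If the 6-month form already has it, say so in the text.
- Section 4.6 and Appendix 12: word the 12-month question as events since the participant was last asked. This also covers someone who missed the 6-month visit.
- Send events reported at 6 months through section 4.7 when they are reported.
- Appendix 12: add event type (ER visit or hospital admission) and number of days hospitalized, to match Appendix 13.

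Under the stated assumptions, the mean lag falls from about 6 to about 3 months. The longest recall falls from about 12 months to 6, or 8 with the visit windows. About 25% of leavers' person-months are recovered. Those who leave before month 6 remain uncovered, and in-system chart review stays at 12 months.

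The cost is a minute or two of intern time at a visit already held, two REDCap fields, a short amendment and a few more events to review. No extra visit or staff is needed.
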